1.3. Rationale for the clinical study and study design

A Phase IIa study (ABX464-101) aimed at evaluating the efficacy and safety of ABX464 given at a fixed dose of 50mg once daily versus Placebo in Patients with Moderate to Severe Active Ulcerative Colitis who have failed or are Intolerant to immunomodulators, Anti-TNF α or Corticosteroids was conducted in Belgium, France, Germany, Austria, Poland, Hungary.

32 patients were randomized (23 ABX464 patients/9 placebo). The principal study results are presented below.

A strong efficacy signal was observed with ABX464 50 mg:

- Clinical Remission rate of 35.0 % of ABX464 patients (Placebo = 11.1%)
- Endoscopic improvement rate of 50.0 %* (p=0.03) of ABX464 patients (Placebo = 11.1%)
- Clinical Response rate of 70.0 % of ABX464 patients (Placebo = 33.0%)

Same results were also observed in Total and Partial Mayo Score, as depicted in the following graphs

[figure not shown]

Figure 5: Mean change in Total and Partial Mayo in ABX464-101 study

At the end of the completed 2 months induction treatment study, 22 Patients (15 previously treated with ABX464 and 7 on placebo) were enrolled into the open-label maintenance study with ABX464 50mg daily (ABX464-102) regardless of what treatment they had previously received. An interim analysis of this maintenance study was performed after all patients had completed at least 12 months dosing in the maintenance study, with a mean ABX464 treatment duration in the maintenance study of 422 days.

The interim analysis used the Month 12 Per Protocol (M12 PP) dataset which included all subjects that had a Month 12 visit. Of the 22 subjects, 3 subjects were excluded from the M12 PP Set: 2 subjects from the ABX464 induction group (one who withdrew due to lack of efficacy at M1 of the maintenance study and one who was lost to follow-up) and 1 subject from the placebo induction group (grade 2 headache at month 4), resulting in 19 subjects analyzed in the efficacy M12 PP set at baseline. Of the nineteen subjects in the set, sixteen had had a Month 12 endoscopy performed which forms part of the Total Mayo score (TMS).

Clinical remissions obtained at the end of the induction study were durable and the rates further improved during the maintenance phase, as additional subjects achieved clinical remission during 12 months treatment.

All patients who had an endoscopy performed, had an endoscopic subscore of 0 or 1. 12/16 patients were in clinical remission at month 12.

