2.4. Secondary Endpoints

The secondary endpoints of this study are:

- Number and rate of patients in clinical remission at Week 8, per each intervention/treatment group. Clinical remission, based on the Mayo Scoring system, is defined as stool frequency subscore = 0 or 1 and rectal bleeding subscore = 0 and endoscopy subscore = 0 or 1 (modified to exclude friability).

- Combined number and rate of patients in clinical remission at Week 8 and at Week 16, per each intervention/treatment group.
- Number and rate of patients with clinical response at Week 8 and Week 16 per intervention/treatment group. Clinical Response is defined as a reduction in Mayo Score of at least 2 points and greater than or equal to 30 percent from baseline with an accompanying decrease in rectal bleeding sub-score of greater than or equal to 1 point or absolute rectal bleeding sub-score of less than or equal to 1 point.
- Number and rate of patients with endoscopic improvement, by segment, and number and rate of patients with endoscopic remission, by segment, at Week 8 and at Week 16 (if available) per intervention/treatment group. Endoscopic improvement is defined as a Mayo endoscopic sub score of ≤1 (excluding friability) and endoscopic remission defined as sub score of 0.
- Number and rate of patients with mucosal healing. Mucosal healing is defined as both endoscopic remission and histological remission (Geboes score < 2.0).
- Reduction relative to baseline in stool and rectal bleeding frequency at every study visit by ABX464 dose group and versus placebo.
- Reduction relative to baseline in partial Modified Mayo Score at every study visit and Modified Mayo Score at Week 16 (if available) by ABX464 dose group and versus placebo.
- Reduction relative to baseline in fecal calprotectin and CRP levels at Week 8 and Week 16 by intervention/treatment group.
- Change relative to baseline in miRNA-124 expression in rectal/sigmoidal biopsies at Week 8 and Week 16 (if available) and in total blood at every timepoints by intervention/treatment group.
- The scores and changes from baseline in IBDQ at Week 8 and Week 16 per intervention treatment group.
- Reduction relative to baseline of infiltrate/histopathology (rectal/sigmoidal biopsies) using the Robarts Histopathology Index (RHI), the Geboes and Nancy Histology Scoring Scales at Week 8 and Week 16 (if available) per intervention/treatment group.

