15.2.1. SECONDARY EFFICACY VARIABLES & DERIVATIONS

15.2.1.1. Number and Percentage of Patients in Clinical Remission at Week 8 and Week 16

Clinical remission is defined as:

- A stool frequency subscore = 0 or 1
- A rectal bleeding sub-score = 0
- An endoscopy sub-score = 0 or 1 (modified to exclude friability)

This endpoint will be calculated per treatment arm and presented descriptively.

Percentage of patients in clinical remission at Week 8

$$= \frac{\text{Number of patients in treatment arm with clinical remission at Week 8}}{\text{Total number of patients in the treatment arm}} \times 100$$

Percentage of patients in clinical remission at Week 16

$$= \frac{\text{Number of patients in treatment arm with clinical remission at Week 16}}{\text{Total number of patients in the treatment arm at Week 16}} \times 100$$

Percentage of patients in clinical remission at Week 8 or Week 16

$$= \frac{\text{Number of patients in treatment arm with clinical remission at Week 8 or Week 16}}{\text{Total number of patients in the treatment arm at Week 8 or Week 16}} \times 100$$

Number of patients with clinical remission at week8 and not at week 16 as well as number of patients with clinical Remission at Week 16 and not at Week 8 will also be presented.

Document: \\ieddc-vnasc01\BIOSdata\Abivax\ABX464\FZA92720\Biostatistics\Documentation\SAP\ABX464-103_SAP_V2.0_10MAY2021

Author: [REDACTED]

Version Number: 2.0
Version Date: 10May2021

Template No.: CS_TP_BS016 Revision 5

Reference: CS_WI_BS005

Effective Date: 01Apr2018

15.2.1.2. Combined Number and Percentage of Patients in Clinical Remission at Week 8 and Week 16

Clinical remission is defined in Section 15.2.1.1. The number and percentage of patients in clinical remission at both Week 8 and Week 16 will be summarized by treatment arm.

Percentage of patients in clinical remission at Week 8 and Week 16

$$= \frac{\text{Number of patients in treatment arm with clinical remission at Week 8 and Week 16}}{\text{Total number of patients in the treatment arm at both visits}} \times 100$$

15.2.1.3. Number and Percentage of Patients with Clinical Response at Week 8 and Week 16

Clinical response is defined as

- A reduction from baseline in MMS ≥ 2 points, and
- A reduction in MMS $\geq 30\%$ from baseline with a decrease in rectal bleeding sub-score ≥ 1 point or absolute rectal bleeding sub-score ≤ 1 point

This endpoint will be summarized by treatment arm.

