Percentage of patients with clinical response at Week 8 and Week 16

$$= \frac{\text{Number of patients in treatment arm with clinical remission at Week 8 and Week 16}}{\text{Total number of patients in the treatment arm}} \times 100$$

Number of patients with clinical response at week8 and not at week 16 as well as number of patients with clinical response at Week 16 and not at Week 8 will also be presented.

Document: \\ieedc-vnasc01\BIOSdata\Abivax\ABX464\FZA92720\Biostatistics\Documentation\SAP\ABX464-103_SAP_V2.0_10MAY2021

Author: [REDACTED]

Version Number: 2.0
Version Date: 10May2021

Template No.: CS_TP_BS016 Revision 5

Reference: CS_WI_BS005

Effective Date: 01Apr2018

15.2.1.4. Number and Percentage of Patients with Endoscopic Improvement and Remission, by Segment at Week 8 and Week 16

Endoscopic improvement is defined as an endoscopic sub-score ≤ 1 and endoscopic remission is defined as an endoscopic sub-score = 0. The improvement and remission will be summarized by segment (descending colon, sigmoid colon, rectum) as well as overall endoscopic improvement and remission for Week 8 and Week 16.

Percentage of patients with endoscopic improvement (or remission) at Week 8 for segment X

$$= \frac{\text{Number of patients in treatment arm with endoscopic improvement (or remission) at Week 8 in segment X}}{\text{Total number of patients in the treatment arm for segment X at Week 8}} \times 100$$

The percentage of patients with endoscopic improvement or remission at Week 16 for segment X will be calculated similarly for data available at Week 16.

The overall percentage of patients with endoscopic improvement or remission at Week 8 will be calculated as follows:

Percentage of patients with endoscopic improvement (or remission) at Week 8 =

$$= \frac{\text{Number of patients in treatment arm with endoscopic improvement (or remission) at Week 8}}{\text{Total number of patients in the treatment arm at Week 8}} \times 100$$

The overall percentage of patients with endoscopic improvement or remission at Week 16 will be calculated similarly for data available at Week 16.

Number of patients with endoscopic improvement and endoscopic remission, by segment at week8 and not at week 16 as well as number of patients with endoscopic improvement and endoscopic remission, by segment at Week 16 and not at Week 8 will also be presented.

Document: \\ieddc-vnasc01\BIOSdata\Abivax\ABX464\FZA92720\Biostatistics\Documentation\SAP\ABX464-103_SAP_V2.0_10MAY2021

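### The only SAP formula for the clinical response percentage counts clinical remission, so followed as written it understates response

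*SAP*

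**What the plan says.** Protocol 2.4 lists the endpoint as "Number and rate of patients with clinical response at Week 8 and Week 16 per intervention/treatment group". The matching objective in Protocol 2.2 covers response at Week 8 and, if available, at Week 16. Protocol 2.4 uses the word combined only for remission.

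SAP 15.2.1.3 is headed clinical response. Its definition begins "A reduction from baseline in MMS" of at least 2 points. It adds a reduction of at least 30%, with either a fall of at least 1 point in the rectal bleeding sub-score or a sub-score of 1 or less. One formula follows, with these parts:

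- Label: "Percentage of patients with clinical response at Week 8 and Week 16".
- Numerator: "Number of patients in treatment arm with clinical remission at Week 8 and Week 16".
- Denominator: "Total number of patients in the treatment arm".

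The sentence after the formula adds a separate count, "Number of patients with clinical response at week8 and not at week 16", and its reverse.

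Remission is a different endpoint. SAP 15.2.1.1 defines it as stool frequency 0 or 1, rectal bleeding 0 and endoscopy 0 or 1, and gives separate Week 8 and Week 16 formulas. The both-visits remission endpoint is in SAP 15.2.1.2, which uses the same numerator string as the response formula and explains it: "The number and percentage of patients in clinical remission at both Week 8 and Week 16 will be summarized by treatment arm".

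**The concern.** The label and the numerator of the response formula name different endpoints, and no reading reconciles them. The numerator matches that of the section just before it, so a copying slip is the likely cause.

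Response is a protocol secondary endpoint. It appears in the estimand table (SAP 2.3) and in the list of variables for between-arm analysis (SAP 15.2.3.1). A formula in the SAP is what a programmer codes. If this one is followed, a table headed response reports remission. If it is corrected silently after unblinding, the choice of numerator, visit and denominator is no longer pre-specified.

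**Working it through.** No stated figure in either document depends on this formula, so there is no plan result to reproduce. The check has four steps.

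**1. Is remission a subset of response?** Inputs: the two SAP definitions; entry MMS of 5 to 9, or 4 under the original protocol (SAP 5.2.4); baseline endoscopy sub-score of at least 2.

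- The highest MMS a patient in remission can have is 1 + 0 + 1 = 2.
- From baseline 5, the smallest reduction is 5 − 2 = 3 points, or 3/5 = 60%.
- From baseline 4, the smallest reduction is 4 − 2 = 2 points, or 2/4 = 50%.
- Both meet the limits of 2 points and 30%, and a bleeding sub-score of 0 meets the bleeding condition. Higher baselines give larger reductions.

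Every remitter is therefore a responder. Listing all combinations of baseline and follow-up sub-scores confirms it:

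| Baseline MMS | Pairs | Remission | Remission and response | Response without remission |
|---|---|---|---|---|
| 5 or more | 1,472 | 92 | 92 | 471 |
| 4 or more | 1,792 | 112 | 112 | 496 |

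These are score combinations, not patients. They show that the subset is strict, not how common each state is.

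**2. One visit or both?** In SAP 15.2.1.2 the same string means both visits, and the counts of response at one visit but not the other fit a joint main formula. On the other side, the heading of SAP 15.2.1.1 uses the same Week 8 and Week 16 phrase for separate rates. The both-visits reading is probable, not established.

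**3. What would the both-visits numerator contain?** Week 8 remission requires an endoscopy sub-score of 0 or 1. Protocol 3.1.1 and SAP 3.1 schedule the Day 113 endoscopy only for a Day 57 sub-score of 2 or 3. None of the Week 8 remission states qualifies. SAP 7.3 gives imputation rules for Week 8 components only. The numerator is then close to zero in every arm, barring an off-schedule endoscopy or a carry-forward rule that the SAP does not state.

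**4. Scale of the word error at a single visit (illustration).** Inputs: Phase IIa rates from Protocol 1.3 and 61 patients per arm (SAP 3.1). Assumption: the Phase IIa rates apply here.

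| | ABX464 | Placebo | Difference |
|---|---|---|---|
| Response | 61 × 0.700 = 42.7, about 43 | 61 × 0.330 = 20.1, about 20 | 70.0 − 33.0 = 37.0 points |
| Remission | 61 × 0.350, about 21 | 61 × 0.111 = 6.8, about 7 | 35.0 − 11.1 = 23.9 points |

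**The case against.** The strongest reply is that the slip is visible in context and the rest of the SAP is sound. The heading, definition, label and following sentence all say response. A reader might infer that the Week 8 response rate will never be produced, and the documents do not support that:

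- SAP 15.2 requires number, percentage and confidence interval for all categorical secondary variables at each timepoint.
- The estimand table in SAP 2.3 covers remission or response at Weeks 8 and 16.
- SAP 7.3 and 15.1.2 already count missing Week 8 data as non-response.
- SAP 15.2.3.1 lists clinical response for analysis.
- The counts of response at one visit only require response status at each visit.

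This stands. A careful programmer may well produce the right Week 8 rate. What remains is that the only explicit response formula contradicts that text.

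A reader might also take the fall from 37 to 24 points as the effect of the formula. It is not. It compares two endpoints at a single visit in a study of 32 patients (23 on drug, 9 on placebo), whereas the formula on its likelier reading concerns both visits.

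Nor should importance be overstated. Response is one of many secondary endpoints, and the stratified test in SAP 15.2.3.2 is for Week 8 remission. The output templates are not in the documents, so no error in a table shell can be asserted.

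**Conclusion.** The formula in SAP 15.2.1.3 is wrong as written and should be corrected. It counts remission under a response label, and because remission is a strict subset of response the error runs in one direction, towards too low a rate. That conclusion rests only on the SAP definitions and the permitted baseline MMS.

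The size depends on the reading. At a single visit, the Phase IIa rates suggest that the reported figure would be half the true rate on drug (35.0% for 70.0%) and about a third on placebo (11.1% for 33.0%), as an illustration only. Read as both visits, the numerator is close to zero in every arm, given the conditional Day 113 endoscopy and no imputation at Week 16.

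The defect is confined to one secondary endpoint. The primary analysis, the order of dose testing and the sample size do not use this formula.

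Correcting the word alone is not enough. Response is defined on the MMS, which needs an endoscopy, so Week 16 response has no stated derivation for patients whose Day 57 result means that no Day 113 endoscopy is scheduled.

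**What to change.** In SAP 15.2.1.3, replace remission with response in the numerator and give one formula per visit:

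- **Week 8:** patients meeting the 15.2.1.3 definition at Week 8, divided by all Full Analysis Set patients in the arm. Missing Week 8 data count as non-response; SAP 7.3 already says so and needs only a cross-reference.
- **Week 16:** patients meeting the definition at Week 16, divided by a stated denominator, with a stated analysis rule for patients who have no Day 113 endoscopy.
- **Both visits:** if this rate is wanted, label it as an additional summary, with the same Week 16 rule.

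Check the response output template against the corrected text. The cost is a short SAP revision and, if needed, a matching change to one template, made before unblinding. No new data are required.

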3.1.1. Design and methodology

This phase IIb study will evaluate the efficacy and the safety of 3 dose-levels of ABX464, administered daily in improving Modified Mayo Score (MMS) in patients with moderate to severe Ulcerative Colitis at Week 8.

Eligible patients will be randomized into 4 parallel intervention/treatment groups:

Intervention/treatment Active Arm	
Group #1: 25mg qd	1 capsule of 25mg ABX464 + 1 capsule of Placebo
Group #2: 50mg qd	1 capsule of 50mg ABX464 + 1 capsule of Placebo
Group #3: 100mg qd	2 capsules of 50mg ABX464
Group #4: Placebo	2 capsules of Placebo

The study design is presented below:

At Week 16, regardless of their clinical/symptomatic response and the actual treatment/dose received, patients willing to continue the study treatment and eligible for enrollment will roll over in an Open Label Extension study (ABX464-104). In this extension study, all patients will be dosed with ABX464 50mg QD. ABX464-104 is a separate clinical protocol subject to health authorities and ethics committee approvals.

In the present induction study (ABX464-103), randomization will be stratified according to the following factors:

- 1) US versus non-US patients
- 2) patients without previous exposure to biological or JAK inhibitors versus patients with previous exposure to biological drugs or JAK inhibitors.

The proportion of patients with previous exposure to biologics or JAK inhibitors will be limited to 60%, including a maximal proportion of patients with previous treatment with vedolizumab of 20%. The maximal proportion of patients with previous exposure with JAK inhibitors will be limited to 10%.

Patients will be treated for 16 Weeks in this induction study. All endoscopies (videos) will be centrally reviewed. E-Diaries will be used to collect frequency of stools, rectal bleedings, number of capsules taken and the intake time.

From Day 1 onwards, randomized patients will be seen at the investigational site on a regular basis (cf. flow-chart).

Flexible sigmoidoscopy with rectal and sigmoidal (if the sigmoidal is inflamed) biopsies will be performed at screening, at Day 57 +/- 4 days (week 8) and at Day 113 +/- 4 days (week 16). The Day 113 measurement will only be taken if patient does not experience endoscopic improvement at Day 57 (i.e.:

endoscopy sub-score of 2 or 3).

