4.2. Eligibility Criteria

4.2.1. Inclusion Criteria

A patient will be eligible for inclusion in this study only if ALL of the following criteria apply:

- Men or women age 18 - 75 years;
- Diagnosis of moderate to severe active UC (including ulcerative proctitis if proximal extension of disease occurs beyond 10 cm) confirmed by endoscopy and histology at least 12 Weeks prior to screening visit. Moderate to severe active UC defined by Modified Mayo Score (MMS) of 5 to 9 inclusive (on a scale of 0-9). Moderate to severe active UC should be confirmed at screening visit with a centrally read endoscopy sub-score of at least 2 (on a scale of 0-3);
- Patients having either a documented inadequate response, no response, a loss of response, or an intolerance (defined as the occurrence of at least one Adverse Reaction leading to treatment discontinuation) to either immunosuppressant treatment (i.e., azathioprine, 6-mercaptopurine, methotrexate), tumor necrosis factor [TNF] inhibitors, vedolizumab, JAK inhibitors and/or corticosteroid treatment. Inadequate response, no response, loss of response is defined as:
 - Active disease or relapse in spite of thiopurines or methotrexate given at an appropriate dose for at least 3 months (i.e. azathioprine 2–2.5 mg/kg/day or mercaptopurine 1–1.5 mg/kg/day in the absence of leukopenia), and/or
 - Active disease despite corticosteroids treatment (prednisolone up to 0.75 mg/kg/day) over a period of 4 Weeks, and/or
 - Active disease or relapse in spite of adequate treatment (as defined in the SmPC) with tumor necrosis factor [TNF] inhibitors or vedolizumab, and/or
 - Active disease or relapse in spite of adequate treatment with JAK inhibitors over a period of at least 6 Weeks.
- Patients receiving oral corticosteroids must have been on a stable dose of prednisone or prednisone equivalent (≤ 20 mg/day) or on beclomethasone dipropionate (≤ 5 mg/day) or on budesonide MMX (≤ 9 mg/day) for at least 2 Weeks prior to the screening visit;
- Topical corticosteroids and topical 5-aminosalicylic acid preparations must have been withdrawn at least 2 Weeks prior to the screening visit;
- Patients who are on oral 5-aminosalicylic acid must have been on a stable dose for at least 4 Weeks prior to the screening visit;

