5.2.1. Screening Visit (Within 28 ± 3 days prior to Day 1)

The screening visit is within 4 Weeks (28 ± 3 days) prior to the first dosing, hence the maximum screening period is 31 days. However, patients can be randomized anytime within the screening window if all examinations are performed as per their schedule and results are available.

The patient will be informed about the general aspects of the study and will sign the screening informed consent form. The patient number will be allocated once the patient is screened in the ITRS. Only when consent has been given may further study procedures be carried out.

During the screening phase, the following assessments will be performed:

- Signed informed consent form;
- Demographic data: year of birth and gender;

- Disease extent (proctitis, left-sided or extensive), duration and disease activity, prior treatment and smoking status;
- Refractoriness to biologics (primary non-response or loss of response);
- Body weight and height;
- Medical history;
- Clostridium difficile (stool antigen and toxin), CMV (IgG and IgM), TB;
- Physical examination and vital signs;
- Hematology and Biochemistry including pregnancy test for all women of childbearing potential;
- 12 leads ECG;
- Sigmoidoscopy with rectal and sigmoidal (if the sigmoid is inflamed) biopsies (within 14 days prior to randomization/baseline); central read results must be available before randomization;
- Record endoscopy sub-score and transfer videos to central reader;
- Partial Modified Mayo Score (within a week prior to endoscopy) and Modified Mayo Score (once endoscopy is performed);
- Hand over the e-Diary to the patient and instruct the patient how to use it; e-Diary should be collected daily from screening to end of study;
- Record all medications received within 3 months prior to baseline and note if the medication is continuing;
- Record all UC medication without time limitation;
- Adverse Event reporting;
- Inclusion/exclusion criteria will be verified.

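### By-segment endoscopic improvement and remission carry no condition on the screening score, so a segment that was not inflamed at entry counts as a success

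*SAP*

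**What the plan says.** SAP 15.2.1.4 gives one definition for every use of the endpoint: "Endoscopic improvement is defined as an endoscopic sub-score ≤ 1 and endoscopic remission is defined as an endoscopic sub-score = 0". The results are to be "summarized by segment (descending colon, sigmoid colon, rectum") as well as overall. The by-segment percentage has as its numerator "Number of patients in treatment arm with endoscopic improvement (or remission) at Week 8 in segment X" and as its denominator "Total number of patients in the treatment arm for segment X at Week 8". Week 16 is handled the same way on the data available. Protocol 2.4 also defines both endpoints by the score reached, by segment, with no reference to where the segment started.

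Four other provisions bear on which segments are inflamed at entry:

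- Protocol 4.2.1 requires a centrally read endoscopy sub-score of at least 2. It does not state this per segment.
- The same section admits distal disease, "including ulcerative proctitis if proximal extension of disease occurs beyond 10 cm".
- Protocol 5.2.1 records at screening "Disease extent (proctitis, left-sided or extensive), duration and disease activity, prior treatment and smoking status".
- Protocol 3.1.1 calls for "rectal and sigmoidal (if the sigmoidal is inflamed) biopsies", so it foresees a sigmoid that is not inflamed.

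SAP 15.2.3.1 sends the by-segment endpoints to the ANCOVA procedure of SAP 15.1.3. That model contains treatment, previous biologic or JAK inhibitor use, and baseline MMS. It contains neither the baseline score of the segment nor disease extent.

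**The concern.** For the overall score the definition works: everyone enters at 2 or 3, so a score of 1 or 0 at Week 8 means the score has fallen. By segment that link is lost. A patient with disease confined to the distal bowel can have a descending colon with nothing to heal. If it is scored 0 at both visits, it enters the numerator for improvement and for remission without having changed. A segment at 1 throughout enters the numerator for improvement.

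The effect of each dose on improvement and remission by segment is a stated secondary objective (Protocol 2.2, SAP 2.2). In the sigmoid and descending colon the planned percentages would mix healing with disease extent at entry. Rates rise in every arm and the contrast with placebo narrows. Extent is not a stratification factor, so a chance imbalance between arms would feed directly into the contrast.

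The same applies at Week 16. Endoscopy there is limited to patients without endoscopic improvement at Day 57, yet their uninvolved segments would still count as successes.

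**Working it through.** The documents give no rate, sample size or power for the by-segment endpoint, so there is no planned figure to reproduce. The check is a mixture calculation.

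**Inputs**

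- u: share of an arm whose segment already meets the success definition at screening (score 0 or 1 for improvement, 0 for remission). Not in the documents; taken as 20%, 40% and 60%.
- p: success rate among the remaining, involved segments. Assumed 40% on drug and 20% on placebo.
- n: about 58 per arm, from 61 randomized less the 5% dropout in Protocol 9.4 (61 × 0.95 = 57.95).
- Segments that already meet the definition are taken to go on meeting it.

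**Step 1: reported rate.** Rate = u + (1 − u)p in each arm. With the same u in both arms, the difference is (1 − u)(p_drug − p_placebo).

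**Step 2: precision.** For all patients, SE = √[(q_drug(1 − q_drug) + q_placebo(1 − q_placebo))/58], where q is the reported rate. The bracketed sum is 0.48 at u = 20% and 40%, and 0.40 at u = 60%. Restricted to involved segments, the sum is 0.40 × 0.60 + 0.20 × 0.80 = 0.40, divided by 58(1 − u).

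| u | Drug v placebo as written | Difference (points) | Difference/SE as written | Involved per arm | Difference/SE, involved only |
|---|---|---|---|---|---|
| 20% | 52% v 36% | 16 | 0.16/0.091 = 1.8 | 46 | 0.20/0.093 = 2.2 |
| 40% | 64% v 52% | 12 | 0.12/0.091 = 1.3 | 35 | 0.20/0.107 = 1.9 |
| 60% | 76% v 68% | 8 | 0.08/0.083 = 1.0 | 23 | 0.20/0.131 = 1.5 |

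The restricted comparison is the more sensitive one in each row, despite fewer patients.

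**Step 3: other rates.** Protocol 1.3 reports overall endoscopic improvement of 50.0% v 11.1% in the phase IIa study. If those rates held in involved segments, the 38.9-point difference would become 31.1, 23.3 or 15.6 points (38.9 × 0.8, 0.6, 0.4). The odds ratio would fall from 8.0 to 3.7, 2.7 or 2.2.

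**Step 4: imbalance in extent.** Suppose the drug has no effect, p is 20% in both arms, and u is 40% in one arm and 30% in the other. The reported rates are 0.40 + 0.60 × 0.20 = 52% and 0.30 + 0.70 × 0.20 = 44%, a spurious 8 points. With p at 11.1% the gap is 0.10 × 0.889 = 8.9 points.

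**The case against.** The strongest reply is that the by-segment denominator is worded differently from the overall one: it adds a reference to the segment, which the SAP does not explain. It could mean segments reached, scored or involved. The imaging charter and the table templates, which might settle it, are not part of these documents. It is also nowhere stated that an uninvolved segment is given a score of 0. This stands as a limit on certainty. It does not remove the point: nothing in the text supports reading the phrase as segments involved at screening, and if it means scored segments, one scored 0 at both visits is still a success.

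Second, SAP 10 tabulates disease extent by arm, and SAP 15.2.3.1 lists mucosal appearance by segment. A careful reader could spot an imbalance. Those outputs do not correct the percentages or the model.

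Third, the size is assumed throughout. In the 40% case neither analysis reaches 1.96. The calculation also lets no uninvolved segment deteriorate. If the drug prevented spread into such segments, part of the contrast would be recovered. All of this stands.

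Fourth, restricting to involved segments has its own costs. A single cut-off of 2 for both endpoints would discard genuine changes from 1 to 0 and label mild disease as uninvolved. Dropping the all-patient rate would depart from the protocol endpoint and lose sight of new proximal involvement. These objections are right and shape the change proposed.

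**Conclusion.** The gap is in the text of both documents: by-segment improvement and remission depend on the visit score alone, and the entry criterion protects the overall score but not each segment. Where uninvolved segments are scored, the risk difference from placebo shrinks by the factor 1 − u, given equal u across arms and uninvolved segments that stay as they were. On assumed rates of 40% v 20%, that is 16, 12 or 8 points instead of 20.

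A reader might infer that heavy dilution is established, or that the trial's endoscopic results as a whole are compromised. The documents support neither. They give no share of patients with an uninvolved segment and no segment scoring rule. They do expect such segments, in the sigmoid and descending colon more than the rectum, but not in any stated number. The primary endpoint, the dose-testing sequence of SAP 7.4, and overall endoscopic improvement and remission are unaffected. The point concerns the interpretability of one named secondary objective, and it is worth correcting because the correction is cheap.

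**What to change.** In SAP 15.2.1.4 and the by-segment line of SAP 15.2.3.1:

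- Make the treatment comparison for improvement in patients whose centrally read screening score in that segment was 2 or more, and for remission in those with a score of 1 or more. Apply the condition to numerator and denominator, and prespecify both thresholds.
- Report, per arm and segment, the number with a screening score of 0, 1, and 2 to 3.
- Keep the all-patient by-segment rate as a supportive descriptive output. This preserves the protocol definition and still shows segments newly inflamed after entry.
- State what the segment denominator means, and record the change in SAP 3.3.

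Leave the overall endpoints as they are. Screening involvement is fixed before randomization, so restricting on it keeps the comparison between randomized groups.

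The cost is SAP wording, a filter and one extra table, with smaller denominators in the sigmoid and descending colon. It depends on segment scores being held for the screening video. The planned by-segment outputs and central scoring at all time points (Protocol 5.3.7) imply this but do not say so. Protocol 9 requires SAP amendments to be signed before final database lock; after that the restricted analysis should be labelled post hoc.
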